4.7. Subject Completion/Withdrawal Procedures

Participants will be terminated early from the study for the following reasons:

1. The participant elects to withdraw consent from all future study activities including follow up.
2. The participant is “lost to follow up” (i.e., no further follow up is possible because attempts to reestablish contact with the participant have failed).
3. The participant dies.
4. The participant develops a medical condition or is started on a new medication(s) not previously mentioned in the list of prohibited medications that, in the opinion of the investigator, may pose additional risks from participation in the study, may interfere with the participant’s ability to comply with study requirements or that may impact the quality of the data obtained from the study.
5. The participant no longer meets inclusion or exclusion criteria as defined in Section 3.3 or if the participant does not meet the previously defined safety criteria in section 9.4.
6. The study is terminated for any reason.

4.8. Criteria for Screen Failure (for Anakinra Studies)

Participants who do not fulfill the following safety criteria will be considered screen failures and will not be eligible for enrollment into the Anakinra study protocols:

1. Less than or equal to 40% decrease in FEV₁ or FVC from pre-challenge values following EPR or the LPR to cat hair allergen (the target endpoint is a $\geq 20\%$ decrease in FEV₁ from baseline during the EPR and a $\geq 15\%$ decrease in FEV₁ from baseline during the LPR); 2) If albuterol is employed as rescue, FEV₁ must recover to within 90% of baseline value within 20 minutes; 3) Oxygen saturation should remain $\geq 93\%$ throughout the challenge period and must be no lower than 2% of baseline measure;
2. Albuterol for rescue therapy should be required no more than three times within the first hour after challenge
3. Albuterol for rescue therapy should be required no more than three times within 12 hours of discharge.
4. FEV₁ should return to within 90% of baseline value at the study discontinuation visit which occurs within 10 days after allergen challenge.
5. Subjects who require more than 1 dose of oral corticosteroid (prednisone 60 mg) to treat an asthma exacerbation associated with inhalation challenge will be considered screen fails and will not continue.

Subjects who are withdrawn for medical concerns related to the study, such as but not limited to prolonged decreased FEV₁ or persistent wheezing, will be followed by study physicians until resolution of these events. As this is a screening protocol, these subjects will not be replaced.

If following all doses of inhaled allergen challenge a participant remains asymptomatic and FEV₁ drops <10% at the completion of the challenge, that participant will be considered a screen failure and will be monitored for 2 hours post challenge. The participant will be discharged following post-challenge venipuncture with rescue medications, including albuterol with aerochamber and oral prednisone 60 mg, instructions for use of these medications in the event of symptoms related to bronchoconstriction, and contact information for the on-call physician. Subject will resume the protocol beginning with Study visit 4 detailed above.

5 STUDY EVALUATIONS AND MEASUREMENTS

5.1. Allergen challenge procedure:

Immediately prior to allergen challenge, determination of adequate lung function without use of bronchodilating medications for 8 hours will be made via spirometry with FEV₁ of at least 80% of predicted and FEV₁/FVC ratio of at least .70, consistent with lung function of persons with mild intermittent or mild persistent asthma being considered minimal acceptable lung function.

Doses will be administered from a DeVilbiss 646 nebulizer. Each volunteer will inhale 5 breaths from the nebulizer at each concentration starting with diluent control. Each breath is started from resting end-expiratory lung volume (Functional Residual Capacity) and continued until a maximum inhalation is reached. After administration of the control diluent, concentrations of allergen will be administered starting with solutions of 0.31, 0.61, 1.22, 2.44, 4.89, 9.77, 19.5, 39, 78.13, 156.25, 312.5, and 625 BAU/ml via nebulizer. During the inhalation challenge the subject will be under direct observation of a physician experienced in treating asthma. Epinephrine for intramuscular administration and albuterol for inhalation will be immediately available. The challenges will be performed in the Clinical and Translational Research Center (CTRC) of the University of North Carolina at Chapel Hill. Full emergency equipment and nursing personnel are immediately available at this location.

The FEV₁ will be measured prior to and 10 minutes after each aerosol inhalation. Starting with the control (saline diluent) solution, increasing concentrations of allergen will be inhaled at 10-minute intervals starting with 0.31 BAU/ml. The FEV₁ measurement obtained after inhalation of the control solution (saline) will be considered the baseline value. If the FEV₁ has declined by less than 10% of baseline after a given concentration of allergen is inhaled, the next higher concentration of allergen will be given. If after inhalation of an allergen dose, the FEV₁ declines by $\geq 10\%$ but $< 20\%$ from the baseline FEV₁ measurement, spirometry will be repeated every 5 minutes for 15 minutes or until a clear nadir in the decline has been reached. If the nadir after 15 minutes is a decline in FEV₁ of less than 10% of baseline, the next higher concentration of allergen will be given. If, however, the nadir after 15 minutes is a decline in FEV₁ $\geq 10\%$ but $< 20\%$ from the baseline measurement, the previous allergen dose will be repeated. To prioritize the safety of subjects and to prevent severe or precipitous decline in lung function, decisions to repeat doses of allergen (rather than escalate dosing) or perform additional spirometry measurements will be made in real time at the discretion of the supervising physician, who will be physically present throughout the allergen challenge procedure. Once a decline in FEV₁ of $\geq 20\%$ is reached, the challenge will be stopped. These activities are summarized in **Figure 1**. Once the challenge is stopped, FEV₁ will be monitored every 10 minutes for the first hour, then every 30 minutes until 2 hours post-challenge, and then hourly until 10 hours after the last allergen dose.

[figure not shown]

Figure 1. Inhaled allergen challenge schematic.

*At discretion of supervising physician

Oxygen saturation by pulse oximeter will be measured during the challenge and with each spirometric evaluation. The physician responsible for the study will determine if any medication is necessary based on the subject's lung function and symptoms. Vital sign measurements including pulse oximetry evaluation will continue to be performed at hourly intervals during and for 10 hours after the exposure. Oxygen saturation by pulse oximeter will be measured during the challenge and with each spirometric evaluation. All subjects will receive 4 puffs of albuterol 10 hours after allergen challenge. If clinically stable and if FEV1 is approximately within 10% of baseline prechallenge FEV1, subject will be discharged with an albuterol inhaler with aerochamber and a single oral dose of prednisone 60 mg, clear instructions on use of medications in the event of symptoms related to bronchoconstriction, and contact information for the on-call physician. The subject will reside in either a local hotel within 10 miles of UNC or their home if their residence is within a 10 mile radius of UNC.

5.2. Sputum induction procedure:

Prior to sputum induction, subjects will receive 4 puffs of albuterol from an MDI attached to a spacer device. FEV1 and FVC will be measured after this step to determine the post-bronchodilator baseline FEV1 and FVC values. Next, an ultrasonic nebulizer filled with 20 cc of 3% hypertonic saline (inhalation grade for respiratory use only, 3% NaCl) will be set to the maximum output setting and turned on. The subject will be instructed to latch his/her mouth onto the nebulizer mouthpiece and breathe normally (i.e., tidal breaths) for 7 minutes as the saline is nebulized through the mouthpiece in a jet stream and inhaled. The nose will not be occluded for this procedure. The subject will be encouraged to come off the mouthpiece at any time to cough if a sputum sample from the lower airways (i.e. not from the back of the throat) is ready for expectoration. Prior to expectoration, subjects will be asked to blow their nose, rinse their mouth with water, and clear their throat to avoid the inclusion of non-airway fluid samples. The sample will be expectorated into a sterile specimen jar and capped.

Following the measurement of FEV₁ after the first 7 minute inhalation period, the concentration of saline will be increased from 3% to 4%, provided the FEV₁ decrement is < 10% from the post-bronchodilator value. If the FEV₁ falls between 10-20% of the post bronchodilator value, the test will proceed but the concentration of saline will remain the same. If the FEV₁ falls by > 20% or if troublesome symptoms occur, the nebulization will be discontinued, and albuterol will be immediately available if necessary to relieve symptoms. The same procedure will be followed for the final 7 minute inhalation period using 5% hypertonic saline provided the FEV₁ safety parameters described above have been met. The nebulization is stopped after a total of 21 minutes or earlier if a sputum sample of good quality is obtained (i.e. visible sputum plugs).

5.3. Spirometry:

Standard methodology conforming to the American Thoracic Society/European Respiratory Society guidelines for measurement of spirometry will be used²²

5.4. Methacholine Challenge:

This test measures the responsiveness of the airways to a standard cholinergic bronchoconstriction agent. Methacholine challenge testing is a standard clinical procedure to determine airway reactivity in patients with known or suspected airway disease. Subjects will be asked to limit caffeine on the day of testing. Subjects will inhale 5 breaths from the nebulizer at each concentration starting with saline control. Each breath is started from resting end-expiratory lung volume (Forced Residual Capacity) and continued until a maximum inhalation is reached. Increasing (doubling) concentrations are inhaled until the FEV₁ falls by at least 20% from the post saline value, the highest concentration has been inhaled, or the subject experiences discomfort or anxiety sufficient for the investigator or subject to consider further testing unacceptable. Methacholine concentrations will be 0.075, 0.156, 0.312, 0.625, 1.25, 2.5, 5.0, and 10.0 mg/ml. If subjects experience symptoms that do not rapidly and spontaneously remit at the end of the procedure, he/she will receive 4 puffs of an inhaled bronchodilator (albuterol) MDI. If needed an additional 4 puffs or a nebulizer treatment with standard dose albuterol (0.083mg) will be given. The subject will not be discharged until spirometry levels return to baseline.

5.5. Venipuncture:

Blood will be drawn to evaluate a complete blood count with differential and also to determine what genes may play a role in a person's response to allergen challenge. At the time of each venipuncture, up to 50 cc will be drawn, and the total for the study will be 150 cc or less.

5.6. Exhaled nitric oxide measurement:

We will measure the amount of nitric oxide (or exhaled NO, eNO) present in orally expired air. An increased concentration of eNO in exhaled air may be found in normal persons with acute inflammation. Thus, measurement of the concentration of eNO may be useful as an indirect assessment of airway inflammation. Lung production of eNO will be measured by asking subjects to exhale briefly into a mouthpiece.

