4. STUDY PROCEDURES

4.1. Screening/Baseline Visit Procedures:

Potential participants will be initially screened for eligibility through a separate screening protocol (IRB#98-0799).

Within 12 months of completing the screening protocol, they will return for Visit 1. Sensitization to cat as determined by skin testing or IgE levels is not expected to change over the course of 12 months. Participants will have to meet all eligibility criteria at the time of the Baseline Visit. On Visit 1:

1. Consent will be obtained
2. Review of subject's medical history and current medications. Allergy skin prick test results from screening protocol #98-0799 will be included in the history.
3. Vital sign measurements (temperature, pulse, respiratory rate, blood pressure), oxygen saturation, and symptom scoring
4. Urine pregnancy test for women of child bearing potential
5. eNO
6. Spirometry
7. Venipuncture for CBC with Diff, Total and cat hair IgE, cytokines, and gene expression (approximately 50 cc total)
8. Physical exam of the ears, nose, throat and chest
9. Sputum induction
10. Collect nasal epithelial lining fluid (ELF).

After completion of the baseline visit, and if for any reason that subject cannot return for the challenge session in the required time, a repeat baseline visit will be done. At this visit the subject will repeat the following:

1. review history and meds
2. vitals

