4.2. Intervention/Treatment procedures

Visit 2: Methacholine Challenge Day (at least 2 days but less than 2 weeks after the baseline visit V1)

1. Review any change in medical status since last visit
2. Vital signs, oxygen saturation, and symptom score
3. Urine pregnancy test
4. Baseline HRV measurement
5. eNO
6. Spirometry
7. Physical exam of the ears, nose, throat and chest

8. Methacholine challenge if inclusion and exclusion criteria are still met (refer to section 5.4 for methacholine challenge procedure)

Visit 3: Allergen challenge day (24-48 hours after V2)

1. Review any change in medical status since last visit
2. Vital signs, oxygen saturation, and symptom score
3. Placement of the HRV device
4. Placement of the ASSIST devices (cardiac electrodes and wrist band)
5. eNO
6. Collect nasal ELF
7. Spirometry
8. If inclusion and exclusion criteria are still met, allergen challenge will be performed as described in section 5.1.
 - a. If subject is asymptomatic and FEV1 drops $<10\%$ at the completion of allergen challenge, subjects will be monitored for 2 hours post challenge and will be discharged following post-challenge venipuncture with rescue medications (albuterol with aerochamber and oral prednisone 60 mg), instructions for use of these medications if asthma symptoms occur, and contact information for the on-call physician. Subject will resume protocol beginning with Study visit 4 detailed below.
 - b. Any subject whose FEV1 drops $\geq 10\%$ will stay for the 10 hour post-allergen monitoring period as outlined below.
9. Collect nasal ELF after completion of the allergen challenge, either following the dose producing a 20% or greater fall in FEV1 (in early phase responders) or following completion of the highest dose of inhaled allergen (in those who do not exhibit an early phase response).
10. Post-challenge monitoring of vital signs every 10 minutes for the 1st hour, then every 30 minutes until 2 hours post-challenge, then hourly until 10 hours post-challenge
11. Spirometry when vital signs are obtained
12. eNO hourly between 2 and 10 hours post-challenge
13. Collect nasal ELF at 7 hours post-challenge (7 hours after the onset of the early phase response).
14. Venipuncture for CBC with diff, cytokines, and gene expression 10 hours post-challenge (approximately 50 cc total)

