15. All subjects will receive 4 puffs of albuterol 10 hours post-challenge. Spirometry will be performed 15 minutes after albuterol if post-challenge FEV1 at 10 hours was not approximately within 10% of baseline.
 - a. Albuterol will be repeated every 20 minutes up to three doses if repeat FEV1 is not within approximately 10% of baseline value or if subject remains in distress.
 - b. If needed, after three inhaled albuterol treatments, additional medications, including nebulized albuterol, atrovent and oral prednisone 60mg, will be given per physician discretion.
16. Subjects will be discharged 10 hours following allergen challenge when clinically stable and when FEV1 is within approximately 10% of baseline FEV1. HRV monitoring will be discontinued prior to discharge. At discharge, all subjects will be provided with an albuterol inhaler and aerochamber, a single dose of oral prednisone 60 mg, clear instructions for use of rescue medications in the event of symptoms related to bronchoconstriction, and contact information for the on-call physician. Subjects will reside overnight at their home if their residence is within 10 miles of UNC or a local hotel within 10 miles of UNC.

Visit 4: 24 hours post challenge

1. Vital signs, oxygen saturation, and symptom score
2. eNO
3. Spirometry
4. Venipuncture for CBC with Diff, gene expression, cytokines (approximately 50 cc total).
5. Methacholine challenge.
6. Sputum induction.
7. Collect nasal ELF.

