6.2. Secondary Endpoint

In addition to identifying subjects for participation in the planned studies of Anakinra vs placebo for mitigating features of asthma exacerbation, the additional purpose of this study is to determine if IL-1 β concentrations in the sputum at baseline before challenge are predictive of key asthma outcomes following inhaled allergen challenge

- 1) Baseline sputum IL-1 β concentration (pg/mL)
- 2) Asthma outcomes following allergen challenge as measured by:
 - a). maximum drop in %FEV1 during LPR
 - b). Change in methacholine reactivity from baseline pre-allergen measurement to 24 hours after allergen challenge.
 - c). exhaled nitric oxide (eNO) level
 - d). induced sputum:
 - i. Granulocyte (neutrophils/eosinophils) numbers and percentages
 - ii. Mucins (secretion of MUC5AC and MUC5B determined by Western blot and ELISA)

Exploratory Endpoints

Additionally, as exploratory endpoints, we will assess the effects of allergen challenge on markers of systemic inflammation and changes in inflammatory gene expression as described below:

- a). **venipuncture** for assessment of systemic inflammatory markers (CBC with differential for absolute neutrophil count and absolute eosinophil count), pro-inflammatory cytokine levels such as IL-1 β , IL-6, IL-8).
- b). **nasal ELF** for assessment of inflammatory mediators associated with allergen-induced airway inflammation.
- c). **gene array analysis** from blood and induced sputum at the baseline visit, again on the day of the challenge and, finally, at 24 hours post challenge. To identify signaling pathways potentially impacted by allergen challenge, we will use Nanostring® technology to measure differential expression of a panel of 594 immunology-related genes. This will be accomplished by collecting and isolating peripheral blood mononuclear cells from venous blood samples collected before allergen challenge, during allergen challenge, and 24 hours after allergen challenge.
- d). **heart rate variability** measurement via commercially-available monitor (Space Labs, Inc). We will identify if specific cardiac changes occur during allergen-induced asthma exacerbation.

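### As listed, the 24-hour nasal lining fluid sample follows methacholine and sputum induction, so it has no fully matched comparator among the other four nasal samples

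*Combined protocol and SAP*

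**What the plan says.** Section 4.1 lists the Visit 1 steps by number, ending with "9. Sputum induction" and then "10. Collect nasal epithelial lining fluid (ELF"). Section 4.2 lists Visit 4 in the same way: "5. Methacholine challenge", then sputum induction as item 6 and nasal ELF as item 7.

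Visit 3 has three ELF collections. Item 6 comes after exhaled nitric oxide (eNO) and before spirometry and the challenge. Item 9 comes at the end of the challenge. Item 13 reads "Collect nasal ELF at 7 hours post-challenge (7 hours after the onset of the early phase response"). Neither methacholine nor sputum induction is scheduled at Visit 3, and the procedures table in Section 15.1 agrees.

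Section 5.2 describes sputum induction: albuterol first, then up to 21 minutes of hypertonic saline by mouthpiece with the nose left open. It adds this instruction: "Prior to expectoration, subjects will be asked to blow their nose, rinse their mouth with water, and clear their throat". Section 5.10 describes ELF collection as a saline spray into each nostril followed by a filter strip. It sets no interval after other procedures and no rule on nose-blowing.

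Section 6.2 makes nasal ELF an exploratory endpoint, "for assessment of inflammatory mediators associated with allergen-induced airway inflammation". Section 6.3 does not name ELF among the exploratory analyses and does not say which sample is its baseline.

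**The concern.** The strips absorb fluid from the front of the nose. Two of the five samples are listed after a procedure in which subjects blow their nose, and one of those two also follows methacholine. The other three follow neither. If either procedure changes what the strips recover, a comparison across visits reads that change as an effect of allergen or of time. The 24-hour sample is the most exposed. An apparent fall from the Visit 3 pre-challenge sample could be read as resolution, and an apparent rise as persistence, when part of it reflects what was done to the subject shortly before sampling. Sampling condition and time point change together for every subject who follows the schedule, so adjustment cannot separate them in that contrast.

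**Working it through.** The plan gives no figure on this point, so the check sets the visit lists side by side and counts contrasts.

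**Condition of each sample, in listed order**

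| Sample | Sputum induction (with nose-blowing) earlier that visit | Methacholine earlier that visit |
|---|---|---|
| Visit 1 (item 10) | yes (item 9) | no |
| Visit 3, pre-challenge (item 6) | no | no |
| Visit 3, end of challenge (item 9) | no | no |
| Visit 3, 7 hours (item 13) | no | no |
| Visit 4, 24 hours (item 7) | yes (item 6) | yes (item 5) |

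The Visit 2 methacholine challenge is 24 to 48 hours before Visit 3, so it is not a same-day exposure there.

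**Contrasts.** Five samples give 5 × 4 / 2 = 10 pairs.

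- Within Visit 3: 3 × 2 / 2 = 3 pairs. None differs in either procedure.
- Visit 1 against Visit 4: 1 pair. Both follow induction; only Visit 4 follows methacholine.
- A Visit 3 sample against Visit 1 or Visit 4: 3 × 2 = 6 pairs. All six differ in induction and nose-blowing, and the three involving Visit 4 also differ in methacholine.

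So 3 of 10 contrasts are matched on both procedures, 6 of 10 differ in nose-blowing, and 6 + 1 = 7 of 10 differ in at least one procedure. Visit 4 enters four contrasts, and none of the four is matched on both.

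**How well Visit 1 and Visit 4 match.** Only nominally. Under Section 5.2 the saline concentration depends on the fall in FEV1. Nebulization can also end before 21 minutes, either because a good sample has been obtained or because FEV1 has fallen too far. Allergen challenge the day before could alter these, so induction exposure need not be equal at the two visits.

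**Omitted procedures.** Section 9.4 lets the covering physician leave out sputum induction and methacholine for a subject whose respiratory status makes them risky. With ELF listed last at Visit 4, such a subject gives a nasal sample without the preceding procedures while the others give one after both. Sampling condition could then depend on the severity of the response.

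**The case against.** The strongest reply is that most of the time course is safe. Visit 3 has its own pre-challenge sample, so the change up to 7 hours can be measured without either procedure intervening. Visit 1 supplies a comparator for 24 hours that also follows sputum induction. If Visit 3 samples are compared within Visit 3, and Visit 4 with Visit 1, nose-blowing is nominally balanced and methacholine is the main remaining difference. This stands. A reader might infer that the whole nasal time course is confounded, or that a 7-hour rise could be produced by nose-blowing alone. The second would need Visit 1 as the 7-hour baseline, and the plan does not name it as such.

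It is also fair that no sentence makes the numbering binding. The Visit 3 list is broadly chronological, but its monitoring items run to 10 hours and overlap the 7-hour sample. Reading the lists as a sequence is reasonable but remains an inference. If the order is not binding, the sampling condition is left uncontrolled, and one sentence is still needed.

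Nor do the documents say that nose-blowing, saline or inhaled methacholine changes nasal mediators, or in which direction. The saline is taken by mouth, so an open nose does not by itself show nasal exposure, and every ELF collection begins with its own nasal spray. A reader might want a false-positive rate. One can be calculated only by assumption. Take a 20% loss of mediator, a within-subject SD of log change of 0.7, n = 50 and no allergen effect. The shift is −ln(0.80) = 0.223 and the noncentrality 0.223 / (0.7/√50) = 2.25, so a paired t test rejects in about 60% of trials. Across SD 1.0 with n = 25 to SD 0.5 with n = 50, the same loss gives 19% to 87%. Section 6.3 specifies two-sample tests, not paired ones, for exploratory comparisons. With a two-sample t test and an assumed within-subject correlation of 0.5, the 60% becomes just under 30%. These figures illustrate sensitivity to the assumptions; they are not estimates for this trial.

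Finally, ELF is a minor measure. It is absent from the synopsis evaluations, from the exploratory list in Section 2.2 and from the analysis text. That sets the priority but does not answer the point.

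**Conclusion.** The point holds for contrasts that join Visit 3 to Visit 1 or Visit 4, and most clearly for the 24-hour sample, which has no fully matched comparator. It does not hold for contrasts within Visit 3. For Visit 1 against Visit 4 it reduces to the methacholine difference, plus any difference in how far induction was carried or whether it was omitted. Six of ten contrasts differ in nose-blowing and seven in at least one procedure.

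This rests on two assumptions: that staff follow the listed order, and that at least one of the procedures affects recovered mediators. The first is reasonable. The second is untested in the documents, so the finding is a potential confounder of unknown size and direction. It concerns one exploratory endpoint; the primary endpoint, the secondary endpoints and eligibility for the anakinra trials do not use nasal ELF. Priority is low. It is worth correcting because the correction is nearly free and the problem cannot be fully removed once samples are collected.

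**What to change.** In Section 4.1 (Visit 1) and Section 4.2 (Visit 4), list nasal ELF collection directly after eNO and before methacholine and sputum induction, which is its position before challenge at Visit 3. Add to Section 5.10 a sentence that this order is followed. Introduce the change from a subject's Visit 1 onward, so that no subject has Visit 1 sampled under one order and Visit 4 under the other.

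This aligns Visit 1, Visit 3 pre-challenge and Visit 4 on same-visit procedures, and omission of a later procedure no longer alters the nasal sample. It does not change the fact that the end-of-challenge and 7-hour samples follow earlier collections the same day.

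For subjects already sampled, state in Section 6.3 that the later Visit 3 samples are compared with the Visit 3 pre-challenge sample and Visit 4 with Visit 1. Report the methacholine difference as a limitation, and report which subjects had either procedure omitted at Visit 4.

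The cost is moving two list items and adding a few sentences. No procedure or sample is added and no clinical rule changes.
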